6.4 Criteria for Removal from Study

The Protocol Director may withdraw subjects from the study for one or more of the following reasons: failure to follow the instructions of the Protocol Director and/or study staff; determination that continuing the participation could be harmful to the subject; the study is cancelled or other administrative reasons.

6.5 Alternatives

The alternative is to not participate in the study.

7. STUDY CALENDAR

	Pre-Study	Scan Date	24 to 72 hours Post-Scan	12 months
Informed consent	X			
Demographics	X			
Medical history	X			
⁶⁸ Ga-RM2		X ^a		
⁶⁸ Ga-PSMA11 (\geq 3 days and \leq 2 weeks)		X ^a		
Follow-up call to participant (24 to 72 hours)			X	
Chart review ^b				X

a: Subjects will undergo either ⁶⁸Ga-RM2 PET/MRI followed within 2 weeks by ⁶⁸Ga-PSMA11 PET/MRI, or ⁶⁸Ga-PSMA11 PET/MRI followed within 2 weeks by ⁶⁸Ga-RM2 PET/MRI. After the 1st scan, the 2nd scan will only occur after the follow-up with the patient for the 1st scan, and after a minimum of 3 days have elapsed. This will be repeated approximately 6 months after HDR local treatment, prior to standard of care biopsy to evaluate for residual disease in the prostate.

b: Subjects will be followed by chart review for 24 months from initial scan date. If a subject transfers clinical care from Stanford HealthCare, investigators may request records from the treating physician.

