1. OBJECTIVE

Specific Aims

Aim 1: ^{68}Ga -RM2 PET/MRI and ^{68}Ga PSMA-11 PET/MRI detection of PC. We will investigate the performance of the new GRPr-binding PET radiopharmaceutical, ^{68}Ga -RM2, and compare it to the currently most widely investigated (but not FDA-approved) PC PET radiopharmaceutical, ^{68}Ga PSMA-11, as well as to mpMRI acquired during PET/MRI for the localization and staging of low-risk and intermediate-risk PC. New lesions identified on PET/MRI and not known from prior systematic prostate biopsy will be confirmed by targeted biopsy and GRPr and PSMA status will be evaluated with specific immunohistochemical stains [1, 2].

Aim 2: ^{68}Ga -RM2 PET/MRI and ^{68}Ga PSMA-11 PET/MRI prediction of PFS after local targeted therapy for PC. We will investigate if the combination of the GRPr-binding PET imaging agent, ^{68}Ga -RM2, and the most widely investigated (but not FDA-approved) PSMA-binding PET imaging agent, ^{68}Ga PSMA-11, together with mpMRI can predict PFS after local targeted therapy. We will determine if ^{68}Ga -RM2 PET/MRI and ^{68}Ga -PSMA-11 PET/MRI assessment at 6-months follow-up will predict PFS at 24 months based on standard clinical follow-up (PSA, imaging, tissue diagnosis).

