3.4 Study Timeline

3.4.1 Primary Completion:

The study will reach primary completion 24 months from the time the last subject completes the first scan.

3.4.2 Study Completion:

The study will reach study completion 84 months from the time the study opens to accrual.

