6.3 Follow-up

Active subject participation ends after the 24 to 72 hour Safety Follow-up after the 2nd post-therapy scan. Investigators will follow subjects by chart review for 12 months post-scan to record any standard of care biopsies or imaging results. The investigators will assist with identification of lesions that can be biopsied, based on ⁶⁸Ga-RM2 and/or ⁶⁸Ga-PSMA11 PET/MRI findings.

If a subject transfers clinical care outside of Stanford Healthcare during the chart review clinical follow-up period, investigators will request permission to contact the treating physician.

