Test to be evaluated: All T1w, T2w, DWI and DCE MR images will first be analyzed and graded by two-board certified abdominal radiologists with subspecialty training in body MRI and extensive clinical experience in prostate MRI (Drs. [name] and [name]), before and after treatment. Areas of focally increased ⁶⁸Ga-RM2 or ⁶⁸Ga-PSMA-11 uptake above surrounding background on pre-therapy scans will be evaluated for changes in uptake by Drs. [name] and [name].

Hypotheses

Primary: Change in ⁶⁸Ga-RM2 or ⁶⁸Ga-PSMA-11 uptake from baseline (T0) to 6 months after start of treatment (T1) will predict treatment response better than T0-T1 changes in MRI.

Secondary: T0-T1 change in ⁶⁸Ga-RM2 or ⁶⁸Ga-PSMA-11 uptake will predict progression-free survival (PFS) better than MRI.

Statistical Analysis:

Primary: (a) logistic regression of response/non-response at T6 on T1-T0 change in PET/MRI measures; (b) McNemar tests of MRI and PET predictions of T6 response.

Secondary: (a) log-rank tests of PFS time (length of drug response) on patients dichotomized as above/below the median change in PET/MRI measures; (b) Cox proportional-hazards regressions of PFS on amount of T1-T0 change in PET/MRI measures.

Statistical Power and Sample Size: We expect a 70-80% response rate to treatment, and 20% of responders progressing by two years.

A sample size of ~75 responders and ~25 non-responders will provide 90% power at one-sided 5% error to detect sensitivity low as 80% at fixed 90% specificity, and to demonstrate a difference in sensitivities of 10 percentage points (e.g., 80% vs 90%).

Median-change groups of ~40 each among the responders will provide 90% power at one-sided 5% error to detect differences in PFS hazard ratios as small as 2.5.

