10.4 Accrual estimates

We expect the accrual of 20 patients each year for 5 years. This is achievable given our experience with other protocols and the support from the referring physicians, Drs [name], [name] and [name] who run the HDR Brachytherapy Clinic at the Stanford Cancer Institute.

Potential difficulties and limitations: All patients will first be seen by a Stanford Cancer Institute

[figure not shown]

Figure 11: Benign human prostate and high-grade human prostate cancer (Gleason 4+4) were stained with anti-PSMA (Santa Cruz, sc-514444, 1:100 dilution) and anti-GRPR (Abcam, #39883, 1:100 dilution) antibody. Scale bar represents 100 microns

physician and then referred if appropriate on clinical grounds for this study. SCI has a substantial volume of men with PC. We do not anticipate any difficulty in recruiting 100 men at Stanford with PC over the period of the grant since referring physicians from Radiation Oncology are supporting the study. We previously enrolled 10 patients included in a prior PET/MRI pilot study in less than 2 months.

Based on our preliminary experience in patients with PC we do not expect any technical problems. We already hold FDA-approved INDs for ^{68}Ga -RM2 PET imaging (IND # [REDACTED]) and ^{68}Ga -PSMA-11 PET imaging (IND # 128379). We have already imaged 38 PC patients at initial diagnosis

($n=9$) or BCR ($n=29$) with both ^{68}Ga -RM2 PET and ^{68}Ga -PSMA-11 PET. Therefore, we do not anticipate problems enrolling participants in this study.

Lastly, we successfully tested in-house the PSMA and GRPr IHC stains both in benign prostate tissue and PC, as shown in **Figure 11**. Therefore, we do not anticipate issues with the IHC analyses of tissue samples from the enrolled participants.

11. REFERENCES:

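### Chart review stops 24 months after each patient's first scan although the study stays open to month 84, so the secondary PFS analyses forgo about one-fifth to one-half of the events they could obtain

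*Combined protocol and SAP*

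**What the plan says.** Collection of outcome data ends at a fixed point for each patient. Footnote b to the study calendar (section 7) reads "Subjects will be followed by chart review for 24 months from initial scan date". Section 6.3 gives a shorter period, "Investigators will follow subjects by chart review for 12 months post-scan to record any standard of care biopsies or imaging results", without saying which scan starts the clock, and the calendar column for chart review is also headed 12 months. No section extends chart review to study close.

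The study itself runs longer. Section 10.4: "We expect the accrual of 20 patients each year for 5 years". Section 3.4.2: "The study will reach study completion 84 months from the time the study opens to accrual".

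Section 10.2 (Aim 2) lists two secondary PFS analyses: "log-rank tests of PFS time (length of drug response) on patients dichotomized as above/below the median change in PET/MRI measures" and "Cox proportional-hazards regressions of PFS on amount of T1-T0 change in PET/MRI measures". It expects 70-80% of patients to respond and 20% of responders to progress by two years. It claims 90% power at one-sided 5% for a hazard ratio of 2.5, with about 40 responders in each median-change group.

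**The concern.** Reconciling the 12- and 24-month texts in favour of 24 months would not settle this point. Under the longer rule, only the last patients enrolled have as little as 24 months of records available by month 84; the first have nearly 84.

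Log-rank and Cox analyses draw their precision from the number of events, and the plan's own rate produces few by 24 months. The background in section 2.1 adds that the PSA criterion can miss failures early, because regrowing tumour needs time to produce the required rise. The predictor is complete only at the scan about 6 months after HDR, so footnote b leaves about 18 months or less of follow-up after it. At stake is whether the PFS comparison has a reasonable chance of detecting the hazard ratio for which it was sized.

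**Working it through.** **Inputs from the documents.** Accrual of 20 a year for 5 years (10.4); closure at month 84 (3.4.2); chart review to 24 months from first scan (section 7, footnote b); 70-80 responders, from a 70-80% response rate in 100 patients; 20% of responders progressing by two years; hazard ratio 2.5; one-sided 5%; 90% power (10.2).

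**Assumptions.** Uniform entry over months 0-60; time counted from the first scan (the plan does not define the origin of PFS); exponential hazard to month 24; equal groups; records still available after month 24.

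**1. The plan's 90%.** Schoenfeld events needed = 4 × (1.645 + 1.282)² / (ln 2.5)² = 40.8, so 41. Events expected at 24 months = 0.20 × 70 to 0.20 × 80 = 14-16. Power = Φ(ln 2.5 × √d / 2 − 1.645):
- d = 14: 53%
- d = 15: 55%
- d = 16: 57%

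The 90% is not reproduced. Freedman's formula needs 47 events. Comparing 24-month proportions (12.2% v 27.8%, 40 per group) gives 54%, as does a log-rank simulation. Had all 80 responders progressed, power would be 99%.

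**2. Follow-up available.** Mean potential follow-up = 84 − 60/2 = 54 months, or 5,400 patient-months for 100 patients. Footnote b collects 100 × 24 = 2,400 (44%).

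**3. Events if chart review runs to month 84.** Hazard λ = −ln(0.8)/24 = 0.0093 per month. With follow-up t uniform on 24-84 months and the hazard multiplied by k after month 24, events = n × mean[1 − 0.8 × exp(−kλ(t − 24))].

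| Hazard after month 24 | Events, n = 70 / 75 / 80 | Power at HR 2.5 | Share of events forgone at 24 months |
|---|---|---|---|
| Unchanged (k = 1) | 27.1 / 29.0 / 30.9 | 77-82% | 48% |
| Halved (k = 0.5) | 21.1 / 22.6 / 24.2 | 68-73% | 34% |
| Quartered (k = 0.25) | 17.7 / 19.0 / 20.3 | 61-66% | 21% |

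The last column is 1 − (events at 24 months)/(events to month 84); for example 1 − 15/29.0 = 48%.

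**4. Loss to follow-up.** With 5-10% annual loss (assumed), 80 responders and constant hazard, events to month 84 are 25-28 and power is 74-78%.

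**5. A waning hazard ratio.** Take 15 events by month 24 at HR 2.5 plus 14 later ones, and weight the log hazard ratio by events. If the later HR is 1.5, the average log HR is (15 × 0.916 + 14 × 0.405)/29 = 0.670, and power is Φ(0.670 × √29/2 − 1.645) = 56%, barely above the 55% at 24 months. If the later HR is 1.0, the average is 0.474 and power is 36%.

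**6. The 12-month text.** If it runs from the first scan, 75-80 responders give about 8 events and 36-38% power. If it runs from the post-therapy scan (about month 18), they give about 12 events and 46-49%.

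**The case against.** The fixed window matches the question asked. The stated objective is PFS at 24 months, and section 3.4.1 has "The study will reach primary completion 24 months from the time the last subject completes the first scan"; 60 + 24 = 84, so month 84 is simply the last patient's 24-month point. A common window also gives early and late enrollees equal ascertainment. The affected analyses are secondary: the primary Aim 2 analyses are logistic regression and McNemar tests on response, and the registered outcome in section 10.3 counts participants with an assessment obtained. Later events may also relate less to a change in uptake over the first 6 months. Section 2.1 itself gives the PSA criterion a specificity of only about 77% and lists benign causes of a rise.

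Most of this stands. It makes the window a defensible design choice for 24-month PFS and is a reason to keep that as the main PFS result. It does not explain why the log-rank and Cox analyses, with power stated for a hazard ratio, should discard later time that the study is open to collect.

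A reader might infer that more than half of the PFS follow-up is lost. The 3,000 of 5,400 months (56%) is potential calendar time in all 100 patients. Among responders at constant hazard, the uncollected progression-free time from first scan is about 48%. Nor do the documents support a flat statement that half the events are lost: that needs a constant hazard beyond month 24, on which the plan is silent.

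**Conclusion.** The point holds as an inexpensive improvement to a secondary analysis; the fixed window does not contradict the 24-month objective. It forgoes about one-fifth to one-half (21-48%) of the events obtainable by month 84. Extending chart review would raise power at HR 2.5 from 53-57% to 61-82%, depending on the later hazard. This rests on uniform entry, records remaining available, and the hazard ratio of 2.5 persisting. Loss to follow-up lowers the gain, and a waning hazard ratio could remove or reverse it if all time is pooled.

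It would be wrong to conclude that longer follow-up rescues the stated 90%. The most favourable scenario reaches about 31 events against 41, so the power statement needs correcting whichever window is chosen.

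**What to change.** - Reconcile footnote b, the 12-month calendar column and section 6.3, and amend all three so that chart review runs from first scan to study close (month 84), death or withdrawal of consent, with at least 24 months for every patient.
- Keep PFS at 24 months as the main PFS result, in line with the objective.
- Add log-rank and Cox analyses using all follow-up, with a prespecified check on whether the hazard ratio is constant over time, for example by estimating it separately before and after month 24.
- Restate the power in section 10.2 from the expected number of events, with the later hazard and loss to follow-up as stated assumptions.

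The cost is a protocol amendment, consent wording on the length of record review, and more chart-review time for early enrollees. Whether patients already enrolled would need new consent cannot be judged from the documents available. No visits, scans, patients or study duration are added. Late follow-up will be less complete for patients whose care moves, although section 6.3 and footnote b already provide for approaching outside physicians.

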8. ADVERSE EVENTS AND REPORTING PROCEDURES

8.1 Potential Adverse Events

The administration of the radioactive substance will feel like a slight pinprick when given by IV injection. Patients who are claustrophobic may feel some anxiety while positioned in the scanner. Also, some patients find it uncomfortable to hold one position for more than a few minutes. The subjects will not feel anything related to the radioactivity of the substance in their body. Because the radioactivity is very short-lived, the radiation exposure is low. The substance amount is so small that it does not affect the normal processes of the body.

This research study involves exposure to radiation from two (before and after treatment) ^{68}Ga -PSMA-11 PET/MRI. There is no radiation exposure from MRI. The effective dose from one typical maximum of 259 mBq (range: 3 to 7 mCi) administration of ^{68}Ga -PSMA-11 is 6.68 mSv. Therefore, the effective dose from two ^{68}Ga -PSMA-11 PET/MRI is 13.36 mSv, approximately equal to 26% of the limit that radiation workers (eg, a hospital X-ray technician) are allowed to receive in one year.

This research study also involves exposure to radiation from two (before and after treatment) ^{68}Ga -RM2 PET/MRI. There is no radiation exposure from MRI. The amount of radiation from one administration of 140 mBq of ^{68}Ga -RM2 is 4.76 mSv. Therefore, the effective dose from two ^{68}Ga -RM2 PET/MRI is 9.52 mSv, approximately equal to 20% of the limit that radiation workers (for example, a hospital X-ray technician) are allowed to receive in one year.

8.2 Adverse Event Reporting

We do not anticipate hazardous situations for the subjects as a result of this protocol. However, standard of care procedures will be in place for verification of correct radiopharmaceutical dose and route of administration. The study Principal Investigator (PI) or his designee will report all serious adverse events (per 21CFR§312.32) to the Stanford CCTO Safety Coordinator within 10 working days of becoming aware of the event (5 days if the event is life-threatening or resulted in death) using the Adverse Events Communication Form. If the principal investigator determines the unanticipated adverse effect presents an unreasonable risk to subjects, the study will be terminated as soon as possible, but no later than 5 working days after the PI makes the determination and no later than 15 working days after first receiving notification of the effect.

9. REGULATORY CONSIDERATIONS

9.1 Institutional Review of Protocol

The protocol, the proposed informed consent and all forms of participant information related to the study (eg, advertisements used to recruit participants) will be reviewed and approved by the Stanford IRB. Any changes made to the protocol will be submitted as a modification and will be approved by the IRB prior to implementation. The Protocol Director will disseminate the protocol amendment information to all participating investigators.

9.2 Data Management Plan

The CRFs will be stored in a locked office in the Nuclear Medicine clinic. Records will be kept using OnCore.

During the clinical investigation, the Protocol Director will evaluate the progress of the trial, including periodic assessments of data quality and timeliness, participant recruitment, accrual and retention, participant risk versus benefit, performance of trial sites, and other factors that can affect study

outcome. Monitoring of the trial will occur every 8 weeks and a record of monitoring activities will be maintained by the study team.

The Stanford Cancer Institute Data and Safety Monitoring Committee (DSMC) will audit study related activities to determine whether the study has been conducted in accordance with the protocol, local standard operating procedures, FDA regulations, and Good Clinical Practice (GCP). This may include review of regulatory binders, case report forms, eligibility checklists, and source documents. In addition, the DSMC will regularly review serious adverse events and protocol deviations associated with the research to ensure the protection of human subjects. Results of DSMC audits will be communicated to the IRB and the appropriate regulatory authorities at the time of continuing review, or in an expedited fashion, as needed.

10. Statistical Considerations and Evaluation of Results

10.1 Aim 1

Participants: 100 patients with low- or intermediate-risk prostate cancer, as described in the inclusion/exclusion criteria.

Design: Patients will have both ^{68}Ga -RM2 and ^{68}Ga -PSMA-11 PET/MRI, including mpMRI. mpMRI and PET images will each be evaluated separately. For each of the 12 prostate regions, between 1-3 imaging-positive samples will be taken, and 1 sample will be taken from each imaging-negative region.

Outcome measures: Number and location of lesions will be recorded for each modality in each patient. Gold standard will be based on the biopsy of lesions found on ^{68}Ga -RM2 and ^{68}Ga -PSMA-11 PET and prior systematic prostate biopsy, including IHC stains for GRPr and PSMA.

Hypothesis: ^{68}Ga -RM2 and ^{68}Ga -PSMA-11 PET/MRI sensitivity, either alone or in combination, will be higher than that of mpMRI alone.

Reference standard: disease status of a lesion will be defined by biopsy of lesions found on ^{68}Ga -RM2 and ^{68}Ga -PSMA-11 PET and from prior saturation prostate biopsy. Tissue samples will be evaluated for GRPr and PSMA expression as previously reported [1, 2] and results will be compared to imaging findings. For GRPr staining, immunohistochemistry will be performed using standard protocols with primary rabbit polyclonal antibody (OPA1-15619, 1:200 dilution; Affinity Bioreagents, Golden, Colorado). For PSMA, a rabbit polyclonal anti-PSMA antibody (D7I8E; Cell Signaling technology, #12815, 1:100 dilution) will be used following the manufacturer's immunohistochemistry protocol. We already successfully used

these, as shown on page 11.

Drs. [name] (clinical pathologist), [name] and [name] will perform all histopathological analyses. Clinical follow-up will be gold standard if biopsy cannot be done.

Test to be evaluated: All T1w, T2w, DWI and DCE MR images will first be analyzed and graded by two-board certified abdominal radiologists with subspecialty training in body MRI and extensive clinical experience in prostate MRI (Drs. [name] and [name]) using the PI-RADS version 2 scoring system, blinded to the clinical information and pathology. The PET images will be corrected using the attenuation data from the MRI scan, and Drs. [name] and [name] who already have extensive experience with ^{68}Ga -RM2 and ^{68}Ga -PSMA-11 from our clinical trials, will perform blinded and random interpretation of the PET scans. Areas of focally increased ^{68}Ga -RM2 and ^{68}Ga -PSMA-11 uptake above surrounding background will be considered positive for PC (**Figures 9 and 10**). This approach is based on recently published guidelines for standard image interpretation developed for ^{68}Ga -PSMA-11 image interpretation [90]. In addition, semi-quantitative measurements of tracer uptake (SUV_{\max}) will be recorded for each lesion.

Statistical Analysis: The following statistical considerations have the full support of a biostatistician ([name]) within the Department of Radiology, who has been specifically assigned to the project and can provide continuous support throughout the data collection and data analysis process. He has also carefully reviewed the study design and was fully involved in the writing of this grant proposal.

Because there may be multiple lesions per-patient and an indefinite number of non-lesions, the primary analysis will be per-region. Each of the 12 regions will have gold-standard positive or negative information, as well as imaging positive or negative assessments. Predictive accuracy of PI-RADS composite score (mpMRI) and SUV_{\max} PET uptake values will be assessed by ROC analysis using univariable logistic regression for the presence of PC. Areas under the entire ROC curve, and partial area at fixed 90% specificity will be compared. Additional benefit of the other modalities over mpMRI alone will be tested by a multivariable logistic regression. All analyses will be adjusted for clustering within patient.

Statistical Power and Sample Size: Based on our clinical experience at Stanford, we expect an average of 2 PC-positive regions and 10 PC-negative regions per patient. Assuming mpMRI has sensitivity of 80% and specificity of 80-90% [91], a sample size of 1200 regions with 20% prevalence will provide 90% power at 5% error to demonstrate non-inferiority of a PET sensitivity of 90% at 80-90% specificity [62, 92, 93].

The per-lesion analysis will depend on the number of lesions found but will be similar. We will also explore whether specific imaging findings are especially accurate in detection of specific subtypes of PC or prostate regions (i.e., peripheral versus transitional zones). It may also be the case that

predictive failures in imaging may be associated with a particular subtype. Given the small sample, we acknowledge that this analysis will be exploratory.

10.2 Aim 2

Participants: Those enrolled in Aim 1.

Design: Patients will be scanned with both ⁶⁸Ga-RM2 PET/MRI and ⁶⁸Ga-PSMA-11 PET/MRI at six months after initiation of therapy. MRI and PET images will each be evaluated separately.

Outcome measures: Changes in MRI features and/or changes in radiopharmaceutical uptake in lesions will be recorded for each modality in each patient. Gold standard of response to treatment and of PFS will be based on standard clinical follow-up (PSA, imaging, tissue diagnosis including IHC stains for GRPr and PSMA)

Test to be evaluated: All T1w, T2w, DWI and DCE MR images will first be analyzed and graded by two-board certified abdominal radiologists with subspecialty training in body MRI and extensive clinical experience in prostate MRI (Drs. [name] and [name]), before and after treatment. Areas of focally increased ⁶⁸Ga-RM2 or ⁶⁸Ga-PSMA-11 uptake above surrounding background on pre-therapy scans will be evaluated for changes in uptake by Drs. [name] and [name].

Hypotheses

Primary: Change in ⁶⁸Ga-RM2 or ⁶⁸Ga-PSMA-11 uptake from baseline (T0) to 6 months after start of treatment (T1) will predict treatment response better than T0-T1 changes in MRI.

Secondary: T0-T1 change in ⁶⁸Ga-RM2 or ⁶⁸Ga-PSMA-11 uptake will predict progression-free survival (PFS) better than MRI.

Statistical Analysis:

Primary: (a) logistic regression of response/non-response at T6 on T1-T0 change in PET/MRI measures; (b) McNemar tests of MRI and PET predictions of T6 response.

Secondary: (a) log-rank tests of PFS time (length of drug response) on patients dichotomized as above/below the median change in PET/MRI measures; (b) Cox proportional-hazards regressions of PFS on amount of T1-T0 change in PET/MRI measures.

Statistical Power and Sample Size: We expect a 70-80% response rate to treatment, and 20% of responders progressing by two years.

A sample size of ~75 responders and ~25 non-responders will provide 90% power at one-sided 5% error to detect sensitivity low as 80% at fixed 90% specificity, and to demonstrate a difference in sensitivities of 10 percentage points (e.g., 80% vs 90%).

Median-change groups of ~40 each among the responders will provide 90% power at one-sided 5% error to detect differences in PFS hazard ratios as small as 2.5.

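### The two Aim 1 reference-standard sentences omit lesions found on mpMRI and contradict the 12-region sampling plan; if they govern, the sensitivity comparison can tilt toward PET

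*Combined protocol and SAP*

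**What the plan says.** Section 10.1 (Aim 1) describes the truth standard in four places.

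- **Outcome measures:** "Gold standard will be based on the biopsy of lesions found on ^{68}Ga -RM2 and ^{68}Ga -PSMA-11 PET and prior systematic prostate biopsy".
- **Reference standard:** "disease status of a lesion will be defined by biopsy of lesions found on" the two PET scans, and "from prior saturation prostate biopsy". The prior biopsy is *systematic* in the first sentence and *saturation* in this one. The same paragraph makes clinical follow-up the standard where a biopsy is not possible.
- **Design:** "For each of the 12 prostate regions, between 1-3 imaging-positive samples will be taken, and 1 sample will be taken from each imaging-negative region".
- **Statistical Analysis:** "the primary analysis will be per-region", and "Each of the 12 regions will have gold-standard positive or negative information".

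The hypothesis is that the sensitivity of the two PET/MRI scans, "either alone or in combination, will be higher than that of mpMRI alone". So mpMRI is the comparator, yet neither truth sentence names a lesion found on mpMRI.

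The operational sections do not settle the matter. Sections 6.1 to 6.3 list no pre-treatment sampling. Section 6.3 collects standard-of-care biopsies by chart review and has the investigators help to identify lesions for biopsy from the PET/MRI findings. The only biopsy in the Section 7 calendar is the one after treatment.

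**The concern.** A comparison of two tests needs a truth standard that treats the findings of both in the same way. Here the two sentences that define truth send PET findings to biopsy and are silent on mpMRI findings. If they govern, verification is partial and depends on one of the tests being compared. That can make PET look more sensitive when the two are equally accurate, which is the direction of the hypothesis.

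If the Design sampling governs instead, the two sentences misstate it, and two analysts could label the same region differently in the primary per-region analysis. The documents do not say which text takes precedence. What is at stake is the Section 10.1 accuracy analysis. The primary endpoints in Section 2.5 and the outcomes in Section 10.3 count participants with an assessable result and are unaffected.

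**Working it through.** The plan has no figure of its own on this point. Its 90% power statement does not depend on how truth is defined and is not used here.

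**Direction.** Take equal true sensitivity for one tracer and mpMRI, and assume that biopsy of a PET-found lesion is correct. Let q be the share of cancer regions seen by the tracer and not by mpMRI. With equal sensitivity, the share seen by mpMRI and not by the tracer is also q. Under the two sentences, all of the first group enter the reference. From the second group, a region enters only if the other tracer saw it, or if prior biopsy or follow-up identified it. So the apparent difference has numerator q minus something no larger than q. It is zero or positive, and never favours mpMRI.

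**Size.** Inputs:

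- 200 positive regions: 100 patients with an expected 2 each (Section 10.1).
- mpMRI sensitivity 80% (Section 10.1). The same 80% is *assumed* for each tracer, so that any gap is spurious.
- f, the share of positive regions missed by prior biopsy: *assumed* 0.1 to 0.5. Section 2.1 says that systematic biopsy with 6-12 cores under-diagnoses index lesions, but gives no rate.
- *Assumed*: PET and mpMRI errors independent, both tracers feed the reference, and follow-up recovers nothing.

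Formulas:

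- U = share of positives seen by at least one tracer. With independent tracers, U = 1 - 0.2 x 0.2 = 0.96.
- Reference positives = 200(1 - f) + 200 f U.
- Apparent sensitivity of one tracer = 160 / reference positives, since all 160 regions it sees are in the reference.
- Apparent mpMRI sensitivity stays at 80%, because its errors are independent of what enters the reference.

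| Overlap of tracer misses | U | f = 0.1 | f = 0.3 | f = 0.5 |
|---|---|---|---|---|
| Independent | 0.960 | 160/199.2 = 80.3% | 160/197.6 = 81.0% | 160/196.0 = 81.6% |
| Latent correlation 0.8 | 0.871 | 160/197.4 = 81.0% | 160/192.3 = 83.2% | 160/187.1 = 85.5% |
| Complete (one PET read) | 0.800 | 160/196 = 81.6% | 160/188 = 85.1% | 160/180 = 88.9% |

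With independent tracers, the spurious gain is 0.3 to 1.6 points. In simulation (20,000 trials), a McNemar test at z > 1.96 then favours the tracer in about 3-6% of trials, against a nominal 2.5%. McNemar is not the planned Aim 1 test.

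**Specificity side.** Cancers seen only on mpMRI and left out of the reference number 200 f (1 - U) x 0.8 = 6.4 f with independent tracers, or 0.6 to 3.2 regions. If these are labelled negative, they become mpMRI false positives. With 10 negative regions in each of 100 patients, that is at most about 3.2/1000, or 0.3 of a point of mpMRI specificity.

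**Effect of follow-up.** If follow-up identifies a share g of the cancers otherwise left out, f is replaced by f(1 - g) and every gain shrinks.

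**If the Design sampling governs.** Suppose all regions are sampled, with one rule for every region positive on PET or mpMRI. The two groups of size q then enter the reference with the same probability. The numerator becomes zero and so does the tilt.

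**The case against.** The strongest reply is that an unbiased reading stands next to the disputed sentences. The Design sentence samples every region, the analysis text gives every region a result, and the primary analysis is per region, whereas the Reference standard sentence speaks of a lesion. Specific Aim 1 has new PET/MRI lesions confirmed by targeted biopsy, and Section 10.1 says "PET/MRI, including mpMRI. mpMRI and PET images will each be evaluated separately", so PET/MRI may include MRI findings. This is a natural reading and may be what was intended. It does not close the point, because nothing says that it prevails, *imaging-positive* is not defined, and the procedures and calendar list no such sampling.

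Three stronger readings are tempting, and the documents do not support them.

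- **That an mpMRI-only cancer missed by prior biopsy is automatically scored negative.** The follow-up fallback may identify it. The fallback does not cure the problem, though. It covers biopsies that cannot be done, not mpMRI lesions that the sentences never call to be biopsied.
- **That *imaging-positive* means PET-positive only.** The Design paragraph evaluates mpMRI and PET separately, and nothing limits the term to PET.
- **That the bias is large.** The lower rows of the table need overlapping tracer misses, and their right-hand cells also need half of the positive regions missed by prior biopsy. No source for either is given. Section 2.1 reports GRPr expression to be independent of PSMA expression, which points to the top row. It does not prove that row, since independent expression does not guarantee independent misses on imaging.

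**Conclusion.** The contradiction is real and should be resolved before the Aim 1 analysis. Two sentences define truth without the comparator's findings. They disagree on the prior biopsy, and they conflict with the sampling and analysis text in the same section.

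The tilt is conditional. It arises only if those two sentences govern, and from equal true sensitivity it can only run toward PET. Its size cannot be derived from the documents. The illustrative 0.3 to 1.6 points rests on 80% sensitivity per read, independent errors, correct targeted biopsy, both tracers feeding the reference, 10-50% missed by prior biopsy and no recovery through follow-up. It is larger if the tracers miss the same cancers, smaller if follow-up recovers some, and zero under even-handed 12-region sampling. A reader should not conclude that the trial is shown to be biased, only that its text permits a biased truth standard.

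**What to change.** 1. Reword both reference-standard sentences identically: a region is positive if any core from it shows cancer, whether from the prior biopsy or from the sampling in the Design sentence.
2. Define *imaging-positive* as positive on PET or mpMRI, with the same sampling rule for each, within the 1-3 cores already stated.
3. Use one term for the prior biopsy.
4. Reconcile the Design sentence with Sections 6.1 to 6.3 and 7, so that it is clear whether and when the sampling takes place.
5. Reconcile the follow-up fallback explicitly. If the Design sampling is not done, treat regions whose status rests on follow-up or on no tissue as unverified in a sensitivity analysis, and state that the PET-versus-mpMRI comparison is subject to verification bias.

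The cost is wording, plus slightly less precision in that sensitivity analysis. No biopsies are needed beyond those the Design sentence already states.
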